### 10.5.1 Analyses of Primary Efficacy Endpoint(s)

An overall between-group difference in RFS will be evaluated with a log-rank test and corresponding proportional hazards model without stratification. Sensitivity analyses, using alternate definitions of RFS as defined in [section 4.1.1](#), will be evaluated in the same manner. Additionally, for RFS, a log-rank test and proportional hazards model with stratification by the two randomization factors will also be conducted.

A sensitivity analysis will be performed censoring RFS at the start of all or selected actual adjuvant therapy for melanoma. However, censoring at start of all or selected adjuvant therapy for melanoma may introduce dependent censoring as the ability to receive further adjuvant therapy will likely be correlated with RFS. An inverse probability censoring weighting (IPCW) method (Robins, et al) which may reduce the potential bias will also be used to obtain an estimate of the treatment effect on RFS and may include baseline covariates in [Section 4.2](#).

In order to assess the impact of imbalances in the type of adjuvant therapy, a **stratified** Cox model will be repeated stratifying actual adjuvant systemic therapy (yes vs no). A KM time to event plot for RFS will be generated by 4 groups (Arm 1 with adjuvant systemic therapy, Arm 1 without adjuvant systemic therapy, Arm 2 with adjuvant systemic therapy, Arm 2 without adjuvant systemic therapy), and 2 separate KM plots will be generated by randomized treatment group in subjects with and without adjuvant systemic therapy respectively. If warranted due to actual adjuvant therapy (eg, the planned adjuvant therapy stratification factor is discordant with the actual for > 10% of all subjects), the stratified Cox model analysis will be repeated stratifying on **actual** adjuvant therapy type (**adjuvant systemic therapy with or without radiotherapy vs radiotherapy without adjuvant systemic therapy vs none**).

**To explore the prognostic and/or predictive value of the covariates listed in [Section 4.2](#), univariate and multivariate proportional hazards models without stratification will be used. Subgroup analyses will be evaluated with a log-rank test and corresponding proportional hazards model without stratification.**

### 10.5.2 Analyses of Secondary Efficacy Endpoint(s)

KM estimates will be calculated for RFS, LRFS, RRFS, DMFS, RFS landmarks by year, OS landmarks by year and quartiles. Greenwood's formula ([Kalbfleisch and Prentice, 1980](#)) for standard error will be used to calculate CIs for each group and between-group differences in landmark KM rate estimates. CIs for quartiles of each group will be estimated per Brookmeyer and Crowley ([Brookmeyer and Crowley, 1982](#)) using a

log-log transformation and bootstrap methods will be used to estimate CIs for between-group differences (see [Section B.3](#) for SAS code fragments). For each group the equal-precision band method will be used to calculate a simultaneous confidence band for RFS, LRFS, RRFS and DMFS over the interval from 1 to 5 years ([Nair, 1984](#)) (see [Section B.2](#) for SAS code fragments).

An overall between-group difference in LRFS, RRFS, DMFS, and OS will be evaluated with a log-rank test and corresponding proportional hazard model with or without stratification by the two randomization factors.

Informative censoring due to distant recurrence is expected for LRFS. For LRFS, after considering distant recurrence as competing event, Gray's test ([Gray, 1988](#)) will be performed to assess the equality of cumulative incidence functions between treatment groups, and the subdistribution proportional hazards model ([Fine and Gray, 1999](#)) will be used to calculate treatment HR with 95% CI with or without stratification by the randomization factors. The same sensitivity analysis will be performed for DMFS with censoring considered a competing risk if the subject has a primary reason for ending the study after a local or regional recurrence withdrawal of consent or lost to follow-up. The same analysis will be performed for RRFS with censoring considered a competing risk if the subject has a primary reason for ending the study after a local recurrence of withdrawal of consent or lost to follow-up. Please see [Appendix B](#) for SAS code fragments.

A sensitivity analysis will be performed for LRFS censoring at the start of all or selected actual adjuvant therapy (systemic therapy radiotherapy) for melanoma. However, censoring at start of selected adjuvant therapy (systemic therapy radiotherapy) for melanoma may introduce dependent censoring as the ability to receive further adjuvant therapy will likely be correlated with LRFS. An inverse probability censoring weighting (IPCW) method (Robins, et al) which may reduce the potential bias will also be used to obtain an estimate of the treatment effect on LRFS and may include baseline covariates in [Section 4.2](#). Similar analyses will be performed on DMFS and RRFS.

If warranted due to actual adjuvant therapy (eg, the planned adjuvant therapy stratification factor is discordant with the actual for > 10% of all subjects), the stratified Cox model analysis will be repeated stratifying on **actual** adjuvant therapy type

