8. WITHDRAWAL FROM TREATMENT, PROCEDURES, AND STUDY

8.1 Subjects' Decision to Withdraw

Subjects have the right to withdraw from the study at any time and for any reason without prejudice to their future medical care by the physician or at the institution.

Subjects (or a legally acceptable representative) can decline to continue receiving investigational product and/or other protocol-required therapies or procedures at any time during the study but continue participation in the study. If this occurs, the investigator is to discuss with the subject the appropriate processes for discontinuation from investigational product or other protocol-required therapies and must discuss with the subject the options for continuation of the Schedule of Assessments ([Table 2](#) and [Table 3](#)) and collection of data, including endpoints and adverse events. The investigator must document the change to the Schedule of Assessments ([Table 2](#) and [Table 3](#)) and the level of follow-up that is agreed to by the subject (eg, in person, by telephone/mail, through family/friends, in correspondence/communication with other physicians, from review of the medical records).

Withdrawal of consent for a study means that the subject does not wish to receive further protocol-required therapies or procedures, and the subject does not wish to or is unable to continue further study participation. Subject data up to withdrawal of consent will be included in the analysis of the study, and where permitted, publicly available data can be included after withdrawal of consent. The investigator is to discuss with the subject appropriate procedures for withdrawal from the study.

8.2 Investigator or Sponsor Decision to Withdraw or Terminate Subjects' Participation Prior to Study Completion

The investigator and/or sponsor can decide to withdraw a subject(s) from investigational product and/or other protocol-required therapies, protocol procedures, or the study as a whole at any time prior to study completion.

Subjects may be eligible for continued treatment with Amgen investigational product(s) and/or other protocol-required therapies by a separate protocol or as provided for by the local country's regulatory mechanism, based on parameters consistent with [Section 12.1](#).

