12.4 Investigator Responsibilities for Data Collection

The investigator is responsible for complying with the requirements for all assessments and data collection (including subjects not receiving protocol-required therapies) as stipulated in the protocol for each subject in the study. For subjects who withdraw prior to completion of all protocol-required visits and are unable or unwilling to continue the Schedule of Assessments ([Table 2](#) and [Table 3](#)), the investigator can search publically available records [where permitted] to ascertain survival status. This ensures that the data set(s) produced as an outcome of the study is/are as comprehensive as possible.

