### 3.2 Sample Size

All analyses will be descriptive with no formal hypothesis testing. The primary objective of the study is to estimate the treatment effect, as measured by the hazard ratio of RFS, of talimogene laherparepvec neoadjuvant therapy followed by surgery (Arm 1) compared to surgery alone (Arm 2) in subjects with resectable, stage IIIB to IVM1a melanoma. Approximately 150 subjects will be randomized 1:1 to receive Arm 1 vs Arm 2 stratified by: (i) disease stage (IIIB nodal vs IIIB in-transit vs IIIC nodal vs IIIC in-transit with nodal vs IVM1a), and (ii) planned adjuvant therapy (adjuvant systemic therapy [eg, INF $\alpha$ , ipilimumab] with or without radiotherapy vs radiotherapy without adjuvant systemic therapy vs none). Primary efficacy analysis of RFS will be based on the Intent to Treat Analysis Set. An overall between-group difference in RFS will be evaluated with a log-rank test and corresponding proportional hazards model without stratification. The Kaplan-Meier (KM) method will be used to estimate 1-year, 2-year, 3-year, 5-year, and overall RFS. Subjects who are not confirmed to be disease-free post-surgery (i.e., who do not have an R0 surgical outcome) or who withdraw prior to surgery will be considered a failure at randomization for RFS, RRFS, LRFS and DMFS. The primary analysis for the primary endpoint will occur at the later time of either the occurrence of approximately 64 events (local, regional, or distant recurrence of melanoma or death) or approximately 2 years after the end of randomization. An 80% CI will be estimated for the hazard ratio of RFS. In addition, an 80% CI will also be estimated for the between-arm difference (Arm 1 – Arm 2) in 2-year RFS, i.e.,  $\Delta$  2-year RFS. It is assumed that: (i) RFS is exponential over the first 2 years, (ii) the 2-year RFS for Arm 2 is about 0.60 (Eggermont et al, 2008), and that there will be a 10% exponential probability of drop-out by the primary analysis. Simulations were performed for various scenarios from 0.05 to 0.15 to evaluate the following parameters assuming possible true  $\Delta$  2-year RFS values of 0.10, 0.125, and 0.15: (i) the average  $\Delta$  2-year RFS 80% CI and its width, (ii) the probability that the  $\Delta$  2-year RFS 80% CI is above 0, and (iii) the average number of events at the

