
**Table 2. Study Design Characteristics Example Endpoint Summary Table**

Endpoint	Primary Summary and Analysis Method	Sensitivity Analysis

Key Secondary Endpoints
 
 
• OS
 
• DMFS
 
• LRFS
 
• RRFS
 
	
 
• The same methods described for the primary endpoint.
 
	
 
• Excluding OS, repeat with stratification by two randomization factors.
 
• For LRFS, assess the equality between treatment groups using Gray's test, and estimate treatment HR with 95% CI stratified by the randomization factors using subdistribution proportional hazards model, with distant recurrence as competing risk.
 
• DMFS will be compared with Gray's test and the subdistribution proportional hazards model with censoring considered a competing risk if the subject has a primary reason for ending the study after a local or regional recurrence of withdrawal of consent or lost to follow-up.
 
• RRFS will be compared with Gray's test and the subdistribution proportional hazards model with censoring considered a competing risk if the subject has a primary reason for ending the study after a local recurrence of withdrawal of consent or lost to follow-up.
 

 
• Landmark RFS, LRFS, RRFS, DMFS by year;
 
• Landmark OS by year
 
	
 
• 80% CI for the K-M estimate in the ITT analysis set by randomized treatment arm with s.e. per Greenwood.
 
• 80% CI for the between-arm difference with s.e., per Greenwood.
 
	
 
• Excluding OS, repeat using the alternative endpoint definition #1 in Section 4.1.1.
 

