## B.8 Estimates Crude Cumulative Incidence Function and Test Equality of Cumulative Incidence (Gray's Test)

```
proc lifetest data=dat1;
  time LRFS*Status(0)/eventcode=1;
  strata TRTGRP / order=internal;
  *test for overall difference between groups;

  *strata randomization_strata/group=TRTGRP order=internal;
  * stratified test;
run;

/* The variable Status has three values: 0 for censored observations, 1
for subjects with event of interest (e.g. local recurrence for LRFS),
and 2 for patients who experienced competing risk */
```

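### The DMFS and RRFS competing-risk sensitivity analyses code study exit after a recurrence as a competing event, which makes them an unlabelled best case for drop-outs and not a competing-risk correction

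*SAP*

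**What the plan says.** SAP 10.5.2 begins with LRFS: "Informative censoring due to distant recurrence is expected for LRFS". There the competing event is distant recurrence, analysed with Gray's test and the Fine-Gray model. The section then carries the approach over. It states that this check "will be performed for DMFS with censoring considered a competing risk if the subject has a primary reason for ending the" (the sentence goes on to name two exit reasons, withdrawal of consent and loss to follow-up, when they follow a local or regional recurrence). RRFS gets the same treatment after a local recurrence. SAP Table 2 repeats both rules; its RRFS entry reads "subdistribution proportional hazards model with censoring considered a competing risk if the subject has a primary reason for ending the study after a local recurrence" and lists the same two exit reasons, so this is not a slip in one sentence.

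Appendices B.8 and B.9 give the status codes: 0 for censored, 1 for the event of interest, "and 2 for patients who experienced competing risk".

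SAP 4.1.2.1.2 defines DMFS as distant metastasis or death from any cause and RRFS as regional recurrence or death from any cause. The main analyses of both are Kaplan-Meier, log-rank and Cox with ordinary censoring.

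**The concern.** A competing event rules out the endpoint or fundamentally changes its probability. Distant recurrence is a clinical event, and using it as the competing event for LRFS is reasonable. Withdrawal and loss to follow-up are not clinical events. A subject who leaves after a regional recurrence can still develop distant metastases, and can still die, which is itself part of DMFS and RRFS.

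Status 2 removes these subjects from the event count but keeps them in the Fine-Gray risk set, so they are treated as never having the event. That is the most favourable outcome one could impute to a group that has already relapsed. A check on informative drop-out should ask whether leavers do worse; this one assumes that they do perfectly. The planned IPCW analyses do not fill the gap, because they address censoring at the start of adjuvant therapy only. With no label, the result can be read as a corrected estimate.

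**Working it through.** **Design inputs.** The documents state no figure for these analyses, so the check starts with SAP Table 1, first row. Inputs: 2-year RFS of 0.60 in Arm 2 ("the 2-year RFS for Arm 2 is about 0.60", SAP 3.2), 0.70 in Arm 1, "there will be a 10% exponential probability of drop-out by the primary analysis", 18 months' accrual (Protocol 3.5.1).
- HR = ln(0.70)/ln(0.60) = 0.698 (stated 0.70).
- 80% CI = 0.698 × exp(±1.2816 × 2/√64) = 0.507 to 0.962 (stated 0.51 to 0.96).
- Expected events 64.1 with 10% drop-out by 42 months (stated 64).

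The other two rows also reproduce.

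**Assumptions that the documents do not supply.** Half of first events are local or regional. The DMFS hazard doubles after such a recurrence. A share q = 20% of relapsed subjects is lost, uniformly over 6 months, 2 years or 4 years after recurrence. Leavers carry the same risk as relapsed subjects who stay.

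**True DMFS incidence.** λ = −ln(0.60)/2 = 0.2554 per year; a = λ/2 = 0.1277. Since the post-recurrence hazard is 2a = λ, DMFS survival is e^(−λt)(1 + at).
- 2 years: 1 − 0.60 × 1.2554 = 24.7%.
- 5 years: 1 − 0.2789 × 1.6386 = 54.3%.

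**Shortfall under the planned coding.** The events lost are those that leavers have after leaving. For drop-out L years after recurrence:

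shortfall(t) = q·a·[(e^(−λL) − e^(−λt))/λ − (t − L)e^(−λt)], averaged over L.

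At 5 years with L = 0.25 (the midpoint of 6 months): 0.2 × 0.1277 × [(0.9381 − 0.2789)/0.2554 − 4.75 × 0.2789] = 0.02554 × 1.257 = 0.032. The planned estimate is then 51.1% against a true 54.3%. Ordinary censoring gives 53.4%, and counting drop-out as an event gives 57.7%.

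**Failures at randomization.** SAP 3.2 and Section 11 make non-R0 subjects and pre-surgery withdrawals failures at randomization for DMFS and RRFS. Such subjects cannot become post-recurrence drop-outs. With a fraction π of them and 2-year RFS held at 0.60, λ solves (1 − π)e^(−2λ) = 0.60, giving 0.2027 for π = 10% and 0.1438 for π = 20%; the shortfall is multiplied by (1 − π). For π = 20%, L = 0.25: 0.8 × 0.2 × 0.0719 × [(0.9647 − 0.4871)/0.1438 − 4.75 × 0.4871] ≈ 0.012. Both values of π are assumed.

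| 5-year shortfall, points | lost over 6 months | 2 years | 4 years |
|---|---|---|---|
| π = 0 | 3.2 | 2.2 | 1.3 |
| π = 10% | 2.2 | 1.5 | 0.9 |
| π = 20% | 1.2 | 0.8 | 0.5 |
| ordinary censoring, π = 0 | 0.9 | 0.6 | 0.4 |

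At 2 years the planned shortfall is 0.7 / 0.3 / 0.1 with π = 0 and 0.2 / 0.1 / 0.05 with π = 20%. Varying the local/regional share from 30% to 70% and the hazard multiple from 1 to 4, with π = 0, gives 0.7 to 4.9 points at 5 years.

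**The SAP's own drop-out rate.** Take 10% exponential drop-out by 2 to 3.5 years, at one rate before and after recurrence, with π = 0. The shortfall is 0.0 to 0.1 points at 2 years and 0.6 to 1.0 at 5 years; ordinary censoring gives 0.0. If the rate is two or three times as high after recurrence, the figures are 0.2 to 0.4 and 1.3 to 3.4.

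**Hazard ratio (Arm 1 relative to Arm 2), no true difference, π = 0, simulated.**
- Equal loss: 1.00.
- 10% of relapsed subjects lost in Arm 1 and 30% in Arm 2 (6 months / 2 / 4 years): planned coding 1.10 / 1.06 / 1.04; censoring 1.03 / 1.02 / 1.01; drop-out as event 0.91 / 0.93 / 0.94.
- With 150 × 0.511 = 77 events, SE = 2/√77 = 0.23. The extra shift in the 6-month case is ln(1.095/1.025)/0.228 = 0.3 SE.

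**RRFS.** The trigger is narrower. With local recurrence as 20% of first events, 20% of those lost and π = 0, incidence is 0.1 to 0.3 points too low at 2 years and 0.6 to 1.3 at 5 years.

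**The case against.** The case on the other side is mainly about size, and much of it stands.

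- The larger figures need 20% of relapsed subjects lost soon after recurrence and nobody failing at randomization. The 0.3 SE shift needs a threefold difference in loss between arms, all within 6 months. These are upper-end cases.
- Deaths may still be found: "where permitted, publicly available data can be included after withdrawal of consent" (Protocol 8.1), and "the investigator can search publically available records [where permitted] to ascertain survival status" (Protocol 12.4). If all were found, the 6-month shortfall of 3.2 points would fall to 1.3, assuming 10% of DMFS events are deaths and a death hazard of 0.5 per year after distant metastasis. The SAP does not say how such deaths enter once a subject has Status 2.
- If leavers have only a quarter of the hazard of retained relapsed subjects, the planned coding and censoring are about equally wrong: 52.2% true, 51.1% planned, 53.5% censored (6 months, π = 0).
- SAP 10.5.2 opens with informative censoring, so a purpose is implied for DMFS and RRFS as well. The purpose carries over, but the coding does not serve it.
- Recoding these subjects to Status 0 inside the Fine-Gray model would be no remedy. Death is already part of both endpoints and the SAP names no other competing event for them, so the model would reduce to the planned Cox analysis.

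A reader might infer that the plan favours talimogene laherparepvec. The documents do not say which arm would lose more relapsed subjects, so they support no direction. A reader might also infer that the main DMFS or RRFS results are compromised. They are not: those analyses use ordinary censoring.

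**Conclusion.** The coding is wrong as described. Study exit after a recurrence is possibly informative censoring, not a competing event, and the planned analysis is a best-case imputation without that label. It lies further from the truth than ordinary censoring when leavers have equal or higher risk than relapsed subjects who stay and recurrence does not lower later risk.

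Reach is small. Only sensitivity analyses of secondary endpoints are affected, in a trial with no formal testing. Under the stated assumptions with 20% of relapsed subjects lost, 5-year DMFS incidence is too low by 1.3 to 3.2 points if nobody fails at randomization, 0.9 to 2.2 if 10% do, and 0.5 to 1.2 if 20% do. At the SAP's own drop-out rate it is at most 0.1 points at 2 years and about 1 point at 5 years. Equal loss produces no hazard-ratio bias when there is no true effect. Unequal loss shifts the ratio in favour of the arm with more loss, and further than censoring does. The size rests on assumed post-recurrence drop-out; the coding point does not. This is a point for the sponsor to consider, not a threat to the trial's conclusions.

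**What to change.** In SAP 10.5.2 and Table 2, stop describing withdrawal or loss to follow-up as a competing risk for DMFS and RRFS. Keep the planned Kaplan-Meier and Cox analyses with ordinary censoring as the reference, and show two labelled bounds beside them:

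- worst case: relapsed drop-outs counted as events at drop-out;
- best case: the current coding, stated to mean no later event.

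Say that neither bound is a correction, and how deaths found after withdrawal enter each. Keep Gray's test and Fine-Gray as a competing-risk analysis for LRFS with distant recurrence.

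The cost is a little SAP wording and one extra run per endpoint on data already collected.

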**(adjuvant systemic therapy with or without radiotherapy vs radiotherapy without adjuvant systemic therapy vs none).**

Multivariate proportional hazards models may be used to explore the prognostic and/or predictive value of baseline factors.

The Clopper-Pearson method ([Clopper and Pearson, 1934](#)) will be used to calculate exact CIs for binary endpoints (eg, overall tumor response, response in injected and uninjected lesions, R0 rate, pCR) (see [Section B.1](#) for SAS code fragments). Wilson's score method with continuity correction ([Newcombe, 1998](#)) will be used to calculate an approximate exact CI for between-group differences in binary rates (see [Section B.4](#) for SAS code fragments). Multivariate logistic models may be used to explore the prognostic and/or predictive value of baseline factors.

## **10.6 Safety Analyses**

### **10.6.1 Adverse Events**

The Medical Dictionary for Regulatory Activities (MedDRA) version 19.1 or later will be used to code AEs to a system organ class (SOC) and a preferred term within the SOC. The CTCAE version 3.0 will be used to grade severity of AEs.

Only treatment-emergent adverse events (see [Section 6](#) for definition) will be summarized by treatment received. Subject incidence rates of all treatment-emergent, grade  $\geq 3$ , serious, non-serious, treatment related, serious treatment related, non-serious treatment related, events leading to talimogene laherparepvec withdrawal/delay/less than 4ml volume per administration, events leading to cancel the scheduled surgical removal of the melanoma tumor lesion(s), fatal adverse events and local effects on the lesion (i.e., pain, inflammation and ulceration) as well as adverse events of interest will be tabulated by SOC and PT in descending order of frequency within an SOC. For all treatment-emergent adverse events additional summary tables will also be provided by (1) SOC, PT in descending order of frequency within an SOC and worst CTCAE grade, and (2) PT in descending order of frequency.

In addition, certain categories of adverse events occurring within the talimogene laherparepvec monotherapy period and within the period after the start of the first dose of talimogene laherparepvec of  $10^6$  PFU/mL but before the first dose talimogene laherparepvec of  $10^8$  PFU/mL will be summarized separately by system organ class and preferred term in descending order of frequency. These categories of adverse events include all treatment-emergent adverse events, serious treatment-emergent adverse

events, non-serious treatment-emergent adverse events, talimogene laherparepvec related treatment-emergent adverse events.

Subgroups group analyses for age group (< 65, ≥ 65 and < 75, ≥ 75), sex, and race (white vs not white) will be presented for all treatment-emergent adverse events by system organ class and preferred term by treatment received in descending order of frequency.

Narratives of deaths through either the 30 days after the last dose of talimogene laherparepvec or the surgical resection of melanoma tumor lesion(s), whichever is later, will be provided.

Adverse events after the completion of the surgical resection of melanoma tumor lesion(s) through the 30 days after the last dose of talimogene laherparepvec or the completion of the surgical resection of melanoma tumor lesion(s), whichever is later, will be also be summarized.

A listing of treatment-related AEs reported in long term follow-up will be provided for the final CSR and may be analyzed earlier as part of a program-wide analysis.

